14.2.4 Retention of records

The Principal Investigator of The UNIVERSITY OF MICHIGAN COMPREHENSIVE CANCER CENTER supervises the retention of all documentation of adverse events, records of study drug receipt and dispensation, and all IRB correspondence for as long as needed to comply with national and international regulations. No records will be destroyed until the Principal Investigator confirms destruction is permitted.

14.2.5 Audits and inspections

Authorized representatives of the manufacturer, a regulatory authority, an Independent Ethics Committee (IEC) or an Institutional Review Board (IRB) may visit the Center to perform audits

or inspections, including source data verification. The purpose of an audit or inspection is to systematically and independently examine all study-related activities and documents to determine whether these activities were conducted, and data were recorded, analysed, and accurately reported according to the protocol, Good Clinical Practice (GCP), and any applicable regulatory requirements.

14.2.6 Data Safety and Monitoring Plan

This protocol will adhere to the policies of the UNIVERSITY OF MICHIGAN COMPREHENSIVE CANCER CENTER Data and Safety Monitoring Plan in accordance with NCI regulations.

This trial will be monitored in accordance with the NCI approved University of Michigan Comprehensive Cancer Center Data and Safety Monitoring Plan. The study specific Data and Safety Monitoring Committee (DSMC), consisting of the protocol investigators, data manager or designee, and other members of the study team involved with the conduct of the trial, will meet quarterly or more frequently depending on the activity of the protocol. The discussion will include matters related to the safety of study participants (SAE/UaP reporting), validity and integrity of the data, enrollment rate relative to expectations, characteristics of participants, retention of participants, adherence to the protocol (potential or real protocol deviations) and data completeness. At the regular DSMC meetings, the protocol specific Data and Safety Monitoring Report form will be completed. The report will be signed by the Principal Investigator or by one of the co-investigators. Data and Safety Monitoring Reports will be submitted to the University of Michigan Comprehensive Cancer Center Data and Safety Monitoring Board (DSMB) on a quarterly basis for independent review.

15. STATISTICAL CONSIDERATIONS

15.1 Sample Size

We will accrue and treat 10 patients on this pilot trial. We expect a 2-month survival rate approximating 15% in patients meeting the inclusion criteria with current standard of care. As we believe ruxolitinib may be highly active in this disease and change the current treatment paradigm, we believe the majority of treated patients will be alive at 2 months. Therefore, if 4 or more patients are alive 2 months following diagnosis, this would provide sufficient evidence to pursue ruxolitinib in an expanded cohort of patients in a future study. This design has 80% power to detect a survival rate of 60% versus an estimated survival rate of 15% using a 2-sided test, with 5% type I error. The operating characteristics for design are given in the table below for a range of true values for the probability of survival at 2 months, with at least 4 responders the critical value.

Probability of survival at 2 months following diagnosis	Probability therapy is deemed effective
0.05	0.010
0.15	0.050
0.25	0.228
0.35	0.488
0.45	0.738
0.55	0.901
0.65	0.978

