2.1.1 Primary Endpoint

Overall survival at two months.

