4.1 Inclusion Criteria

Patients must meet all of the following inclusion criteria to be eligible for enrollment:

1. Patients, or their legally authorized representative, must voluntarily provide written IRB-approved informed consent.
2. Males and females, 18 years of age or older at the time of enrollment.
3. Patients must meet the diagnostic criteria for HPS (at least 5 of the following):
 - fever
 - splenomegaly
 - cytopenia involving ≥ 2 cell lines (Hemoglobin < 9 g/dL; platelets $< 100,000/\mu\text{L}$; absolute neutrophil count $< 1000/\mu\text{L}$)
 - hypertriglyceridemia or hypofibrinogenemia
 - tissue demonstration of hemophagocytosis
 - low or absent NK cell activity
 - serum ferritin ≥ 3000 ug/L
 - soluble IL-2 receptor (CD25) > 2400 U/mL.
4. In the investigator's opinion, the patient has the ability to participate fully in the study and comply with all its requirements.

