5. REGISTRATION

All subjects who have been consented are to be registered in an online Database. For those subjects who are consented, but not enrolled, the reason for exclusion must be recorded.

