12.2 Calendar

	Enrollment (within 14 days of treatment)	Pre-treatment (within 48 hours of treatment)	Weekly (weeks 1-5) ⁴ (beginning day 7, +/- 2 days)	q14 days +/- 3 days (weeks 6-12)⁴	q28 days +/- 3 days (>12 weeks)⁴
Informed consent	X				
H&P (including medication review)	X	X	X	X	X
CBC ¹	X	X	X	X	X
Serum Chemistries (including AST/ALT)	X	X	X	X	X
Pregnancy test ⁵	X				
Ferritin	X	X	X	X	X
Lipids	X	X	X	X	
Fibrinogen	X	X	X	X	
sIL-2 Receptor	X	X	X	X	
NK cell activity ²	X	X	X		
Research blood draw ³		X	X		
Collect Adverse Events	X	X	X	X	X

¹Performed at least every 72 hours for weeks 1-5 of treatment. ²May be performed every 7-14 days. If total lymphocytes are insufficient to measure NK cell activity during enrollment, repeat testing is not required. ³Four heparin tubes (≈20 mL total volume) will be collected. Peripheral blood mononuclear cells and platelet-poor plasma will be obtained and cryopreserved for ancillary studies. Research blood draws will cease 14 days after a CR is achieved or after 5 weeks of treatment, whichever comes first. ⁴Study procedures required for response assessments and toxicity monitoring will be performed every two weeks (Bi-weekly) for patients who remain on treatment >6 weeks. For patients who remain on treatment >12 weeks, the following procedures will be performed monthly: H&P, CBC, serum chemistries, ferritin, and adverse events. ⁵Pregnancy testing will be performed every 6 weeks (+/- 7 days) in women of child-bearing potential.

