15.2 Analyses

Primary:

The primary analysis is the count of patients alive after 2 months since study entry. If 4 or more patients are alive at the 2 months assessment, the null hypothesis of a 15% survival probability at 2 months will be rejected in favor of our alternative hypothesis of a 60% survival probability. Ninety-five percent confidence intervals will be constructed based upon the exact binomial confidence interval. No loss-to-follow-up or censoring is expected prior to the study's primary endpoint assessment.

Secondary:

There are no formal response criteria for secondary HPS. Therefore, efficacy assessments (including appropriate laboratory studies) will be performed weekly (weeks 1-5), and every two weeks (weeks 6-12), and monthly (after 12 weeks), and responses determined as previously reported in a retrospective study.⁸ Briefly, a complete response is defined as

complete normalization of all quantifiable symptoms and laboratory abnormalities (described in the diagnostic criteria for HPS, above). A partial response is defined as at least a 25% improvement in two or more quantifiable symptoms/laboratory markers following the initiation of treatment. The best overall response is the best response recorded from the start of the treatment until disease progression/recurrence

Follow-up time will be calculated from the first administration of ruxolitinib, until death for OS or until disease-progression or death for PFS. Patients lost to follow-up will be censored on the date of their last known clinical assessment. Specifically for DOR, only patients having at least a PR to therapy are evaluable. Duration will be calculated from the date of the determination of partial response or better until the date of progression, death, or additional non-protocol therapy. Again, for patients lost to follow-up, duration will be censored at the time of last clinical assessment. The count and percentage of the number having an objective response (CR, CRu, or PR) will be reported along with confidence intervals. Product-limit estimates of Kaplan and Meier will be used to estimate OS, PFS, and DOR. The likelihood of loss to follow-up is expected to be extremely low.

Exploratory:

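### The 4-of-10 go/no-go count runs from diagnosis in 15.1 and from study entry in 15.2; neither date is defined, and secondary OS uses first dose

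*Combined protocol and SAP*

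**What the plan says.** The primary endpoint in 2.1.1 is "Overall survival at two months", with no starting point. Section 15.1 gives the decision rule: "if 4 or more patients are alive 2 months following diagnosis, this would provide sufficient evidence to pursue ruxolitinib". The operating-characteristics table in 15.1 uses the same clock in its column header, "Probability of survival at 2 months following diagnosis". Section 15.2 then says: "The primary analysis is the count of patients alive after 2 months since study entry". It rejects the 15% null at 4 or more survivors, the same cut-off and null as 15.1. For secondary overall survival, 15.2 says: "Follow-up time will be calculated from the first administration of ruxolitinib, until death for OS".

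Neither primary-analysis date is defined:

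- **Diagnosis.** Section 4.1 lists criteria ("Patients must meet the diagnostic criteria for HPS (at least 5 of the following"), but no section says which date counts as the diagnosis date or limits the gap from diagnosis to treatment. The prior-therapy exclusion in 4.2 covers only a recent window and exempts corticosteroids, so patients diagnosed and treated earlier can enter.
- **Study entry.** This could be registration (section 5: "All subjects who have been consented are to be registered in an online Database"), the enrolment column of the 12.2 calendar ("Enrollment (within 14 days of treatment"), or first dose. The term's only other use is for pregnancy-test timing in 12.1.1.

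Section 3.3 replaces subjects who never receive a first dose.

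**The concern.** This count is the protocol's only stated go/no-go criterion. Two people following 15.1 and 15.2 could reach opposite decisions from the same 10 patients, since one reclassified patient is enough to move the count across 4.

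There is also a bias with a known direction. Because undosed subjects are replaced, everyone counted has survived to first dose. A clock that starts earlier includes days on which no counted patient could die, and its 2-month mark falls sooner after dosing. Its count can equal or exceed the first-dose count but never fall below it. The stated 5% type I error therefore holds only if 15% is the right null for the clock actually used, among patients who survived to treatment.

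Which of the two written clocks gives the higher count is not fixed. It is the diagnosis clock if diagnosis precedes entry. It is the entry clock if entry means consent or registration and the fifth criterion is confirmed afterwards.

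**Working it through.** **Inputs from the documents.** n = 10, cut-off 4 or more, null 15% (15.1 and 15.2); design alternative 60% (15.1); enrolment and screening up to 14 days before treatment (12.1.1, 12.2); replacement of undosed subjects (3.3).

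**Step 1: reproduce the plan's figure.** With X the number alive and p = 0.15:

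P(X ≥ 4) = 1 − (0.19687 + 0.34743 + 0.27590 + 0.12983) = 0.04997.

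This matches the 0.050 in the 15.1 table. It leaves no room: the same tail is 0.1209 at p = 0.20 and 0.2241 at p = 0.25.

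**Step 2: assumptions.** The documents give no lags, so these are illustrative: 2 months = 60 days; inert drug; constant hazard with 60-day survival of 15% from first dose.

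**Step 3: same lag in all 10 patients.** If the clock starts t days before first dose, a patient alive at first dose must survive only 60 − t more days, so p(t) = 0.15^((60 − t)/60).

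| t (days) | p(t) | P(X ≥ 4) |
|---|---|---|
| 0 | 0.1500 | 0.0500 |
| 1 | 0.1548 | 0.0553 |
| 3 | 0.1649 | 0.0675 |
| 7 | 0.1872 | 0.0994 |
| 14 | 0.2335 | 0.1870 |

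Tying the 15% to the earlier clock does not remove the effect. Conditioning on survival to first dose gives 0.15 / 0.15^(t/60), which is the same p(t) under a constant hazard.

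**Step 4: lag in some patients only.** With t = 14 in k patients and t = 0 in the rest (exact Poisson-binomial), P(X ≥ 4) is 0.0800 for k = 3 and 0.1055 for k = 5.

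**Step 5: hazard shape.** For a Weibull from first dose with 60-day survival 0.15 and t = 14 in all patients, p = 0.15^((46/60)^shape):

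| Shape | p | P(X ≥ 4) |
|---|---|---|
| 0.5 | 0.1899 | 0.1038 |
| 0.7 | 0.2070 | 0.1335 |
| 1 | 0.2335 | 0.1870 |
| 1.5 | 0.2798 | 0.2975 |

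**Step 6: how often the two written clocks disagree.** The counts are nested, so the probability of opposite decisions is the difference between the two go probabilities (inert drug, constant hazard).

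| Diagnosis, days before dose | Entry, days before dose | Disagreement |
|---|---|---|
| 14 | 0 | 0.1870 − 0.0500 = 0.1370 |
| 14 | 7 | 0.1870 − 0.0994 ≈ 0.0876 |
| 14 | 14 | 0 |
| 0 | 7 | 0.0994 − 0.0500 = 0.0494, entry clock higher |

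**The case against.** The strongest reply is that 15.2 is the analysis section and states origin, cut-off and null in one place, so the reference to diagnosis in 15.1 may be loose drafting. That is plausible, but no section gives 15.2 precedence, and the operating characteristics are stated on the diagnosis clock. Following 15.2 alone would also leave study entry undefined, with up to 14 pre-dose days in the count if it means enrolment.

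Several points limit the size and do stand:

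- The 18.7% figure puts every patient at the full 14 days. In a disease for which section 1.3 cites a median of 35 days from diagnosis to death, that is an extreme case. At 1 to 3 days the figures are 5.5% to 6.7%.
- Nothing in the documents supports a rising hazard, so the top of the Weibull range is sensitivity only.
- Disagreement is smaller if the drug works. At 60% survival under the same model, the go probability is 94.5% from first dose, 96.8% with a 7-day lag and 98.3% with a 14-day lag. The clocks then disagree in 3.8% of trials (diagnosis 14 days before dosing, entry at dosing) or 1.5% (entry 7 days before dosing).
- The case where the entry clock runs higher needs entry to mean consent or registration. Sections 4.1 and 5 separate consent from enrolment, so this reading is less natural, though section 5 does register subjects at consent.
- A different origin for a secondary curve is not in itself an error, and survival from first dose will be reported beside the count.
- A go leads to a further study, not an efficacy claim, and an exact confidence interval accompanies the count.

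These points bear on emphasis and size. The protocol still states a formal null, a 5% error rate and a rejection rule, and it gives that rule two clocks.

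**Conclusion.** The concern holds and should be fixed. Confidence is high that 15.1 and 15.2 conflict, that neither date is defined, and that any clock earlier than first dose can only leave the count unchanged or raise it. Confidence in the size is low because no lags are given. Under a constant hazard with 60 days as 2 months, an inert drug and a 15% null from first dose, the false-positive rate ranges from 5.0% with no lag to 18.7% with 14 days in every patient; at 14 days, Weibull shapes from 0.5 to 1.5 spread it from about 10% to about 30%. These are illustrations, not estimates for this trial. If diagnosis, entry and first dose fall on the same day in every patient, the conflict has no numerical effect, but nothing in the protocol requires that.

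**What to change.** Choose one defined origin other than diagnosis. First dose of ruxolitinib is preferable: it matches secondary overall survival in 15.2 and the replacement rule in 3.3, and it removes pre-treatment survival from the count. A study-entry date is an acceptable alternative if the protocol defines it, but if that date precedes dosing, some pre-dose survival remains. Simply changing 15.1 to match 15.2 would remove the contradiction without settling what study entry means.

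Write the chosen origin identically in 2.1.1, the 15.1 text and table header, and the primary analysis in 15.2. Add one sentence stating that the 15% null refers to that clock. Recompute the cut-off, type I error and table only if the null changes.

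The cost is wording: no added visits, data or patients. The drawback is that a first-dose count may be lower than a count on an earlier clock, so the threshold of 4 may be harder to reach.

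### Section 15.1 states 80% power at 60% survival, but the 4-of-10 rule has exact power 94.5%; the table's 0.05 row is also wrong (0.010 stated, 0.001 exact)

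*Combined protocol and SAP*

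**What the plan says.** Section 15.1 fixes the sample size: "We will accrue and treat 10 patients on this pilot trial". It sets the decision rule ("with at least 4 responders the critical value") and states the power: "This design has 80% power to detect a survival rate of 60% versus an estimated survival rate of 15% using a 2-sided test", at 5% type I error. It then adds: "The operating characteristics for design are given in the table below". That table gives the probability of declaring the therapy effective at seven true survival rates from 0.05 to 0.65. It has no row for 0.60, the rate at which power is claimed.

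Section 15.2 applies the same cut-off: "The primary analysis is the count of patients alive after 2 months since study entry". The condition for success reads: "If 4 or more patients are alive at the 2 months assessment". When it is met, the plan rejects a null of 15% and takes 60% as the alternative. On estimation it says: "Ninety-five percent confidence intervals will be constructed based upon the exact binomial confidence interval". It expects no loss to follow-up or censoring before the primary assessment.

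**The concern.** With 10 patients, a fixed count and no expected dropout, power is a single binomial tail probability that needs no further assumption. The power sentence and the table describe the same rule, so they must agree, and they do not: 80% at 60% survival is lower than the table's own value at 55%.

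Section 15.1 is the only justification of the sample size. Anyone reporting the trial, or planning the follow-on study it mentions, could copy a wrong operating characteristic. A reader who tries to reconcile 80% with a two-sided 5% test might also suspect the cut-off of 4 rather than the power figure, and that would cast doubt on the go/no-go threshold.

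**Working it through.** **Inputs.** n = 10, cut-off 4, null 0.15, alternative 0.60, two-sided 5% and stated power 80% (Section 15.1). Section 15.2 repeats the cut-off, the null and the alternative, and expects no loss to follow-up.

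**Formula.** P(success | p) = P(X ≥ 4) = 1 − Σ C(10,k) p^k (1−p)^(10−k), summed over k = 0 to 3.

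**Step 1: type I error, which reproduces.** At p = 0.15 the terms for k = 0 to 3 are 0.19687, 0.34743, 0.27590 and 0.12983, which sum to 0.95003. So P(X ≥ 4) = 0.04997, as the plan says. All of it is in the upper tail. Because P(X = 0) = 0.197, no low count fits in a 5% rejection region. The minimum-likelihood two-sided exact p-value at 4/10 is therefore also 0.04997.

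**Step 2: power at 60%, which does not reproduce.** At p = 0.60 the terms for k = 0 to 3 are 0.00010, 0.00157, 0.01062 and 0.04247, which sum to 0.05476. Power = 1 − 0.05476 = **0.9452**, against 0.80 stated.

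**Step 3: the plan's own table.** P(X ≥ 4) rises with p, so power at 0.60 lies between the printed 0.901 (at 0.55) and 0.978 (at 0.65). The midpoint is (0.901 + 0.978)/2 = 0.9395. Solving P(X ≥ 4 | p) = 0.80 gives p = 0.4837.

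**Step 4: could 80% come from another calculation?**

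| Reading, n = 10 | Power at 0.60 |
|---|---|
| Exact, at least 4 (the plan's rule) | 0.945 |
| Exact, at least 5 (equal-tailed two-sided 5% test) | 0.834 |
| Exact, at least 6 | 0.633 |
| Normal, null variance, two-sided | 0.930 |
| Same, continuity-corrected | 0.876 |
| Normal, alternative variance, two-sided | 0.828 |
| Arcsine, two-sided | 0.871 |

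The one-sided versions of the four approximations give 0.956, 0.917, 0.896 and 0.926. Nothing falls within 2 points of 80%.

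**Step 5: table rows.**

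| True survival | Stated | Exact | Stated − exact |
|---|---|---|---|
| 0.05 | 0.010 | 0.0010 | 0.0090 |
| 0.15 | 0.050 | 0.0500 | 0.0000 |
| 0.25 | 0.228 | 0.2241 | 0.0039 |
| 0.35 | 0.488 | 0.4862 | 0.0018 |
| 0.45 | 0.738 | 0.7340 | 0.0040 |
| 0.55 | 0.901 | 0.8980 | 0.0030 |
| 0.60 | no row (text: 0.80) | 0.9452 | −0.1452 |
| 0.65 | 0.978 | 0.9740 | 0.0040 |

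The 0.05 row is about ten times too high. A misplaced decimal would explain it, but the documents do not say.

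**Step 6: interval at the cut-off (secondary).** Section 15.2 does not say which exact interval it means.

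| Result | 95% interval | Limits |
|---|---|---|
| 4/10 | Clopper-Pearson | 12.2% to 73.8% (contains 15%) |
| 4/10 | Sterne | 15.003% to 70.9% |
| 4/10 | Blaker | 15.003% to 71.7% |
| 5/10 | Clopper-Pearson | 18.7% to 81.3% |

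The Sterne and Blaker lower limit solves P(X ≥ 4 | p) = 0.05, at p = 0.150028. The mismatch with the rule is thus confined to exactly 4/10, which has probability 0.1115 at 60% true survival and 0.2384 at 45%.

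**The case against.** The strongest reply is that 80% may be a design target: a discrete rule can overshoot its target, and a claim of at least 80% would be true. That reading makes the figure an understatement, and the error is indeed in the safe direction. But the text does not say at least. It assigns 80% to the same design as a table that excludes that value.

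A second reply concerns sidedness. An equal-tailed two-sided 5% test would need at least 5 of 10 (upper tail 0.0099, power 83.4%), so the sentence and the table might describe different designs. The plan does not name its test, and stating it would help. Both sections nevertheless fix the cut-off at 4, and the total rejection probability at 15% is 0.04997 whichever tail it lies in. Even the 5-of-10 test does not give 80%.

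A third reply is that 94.5% holds only with exactly 10 treated patients, while Section 3.2 says up to 10. With the cut-off held at 4, power at 60% is 90.1% with 9 patients and 82.6% with 8. This is a fair caveat, but Section 15.1 bases its calculation on 10. The two sections also differ on the time origin (diagnosis in 15.1, study entry in 15.2). That needs its own attention but does not change the binomial figure.

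Finally, Clopper-Pearson is a legitimate exact interval, and the decision rests on the count. That is right, so the interval point is an optional clarification and not an error.

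**Conclusion.** The concern holds. The stated 80% is wrong for the stated rule: exact power at 60% survival is 94.5%, so the type II error is 5.5% and not 20%. The 0.05 table row should read 0.001. The differences of 0.002 to 0.004 in five other rows have no practical effect, and the 5% type I error is correct in total.

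This rests on 10 treated patients, a cut-off of 4, independent outcomes with a common survival probability, and no loss before 2 months. All but the independence and common-probability conditions are stated in the plan, and those two are implicit in its own table.

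The consequence is limited. The power error is conservative, and the wrong table row lies below the null. The sample size, the cut-off and the go/no-go decision are unaffected. It should be corrected because it is a definite numerical error in the main design statement, and that statement contradicts the table beneath it.

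**What to change.** Keep the 4-of-10 rule, the two-sided 5% test and the 95% interval level.

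- **Section 15.1, text.** Replace the power sentence with: *With the rule of at least 4 of 10 patients alive at 2 months, the design has exact power of 94.5% at a true survival of 60%, with type I error 0.050 at 15%.* Keep the two-sided description beside it, and say that the rejection region is all in the upper tail.
- **Section 15.1, table.** Replace the probability column with 0.001, 0.050, 0.224, 0.486, 0.734, 0.898 and 0.974, and add a 0.60 row with 0.945.
- **Section 15.2, optional.** Name an exact test and 95% interval that agree with the rule: either the minimum-likelihood test with the Sterne interval, or Blaker's test with Blaker's interval. Report the exact p-value beside the interval, because the lower limit at 4/10 rounds to 15.0%. If Clopper-Pearson is preferred, say in advance that at 4/10 it will contain 15% and that the count decides.

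The cost is one sentence and one table column, plus an optional sentence in Section 15.2. Nothing changes in the sample size or the conduct of the study.
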